7.9.5 Vitals signs

Descriptive statistics of subject weight, BMI, vital signs (i.e. pulse rate and both systolic and diastolic blood pressure in supine position) will be tabulated by treatment group for each study visit.

Descriptive statistics will also be reported for the following categorised measurements:

- systolic blood pressure:
 - < 90 mmHg and a decrease of ≥ 20 mmHg
 - > 140–160 mmHg and an increase of ≥ 20 mmHg
 - > 160 mmHg and an increase of ≥ 20 mmHg
- diastolic blood pressure:
 - < 60 mmHg and a decrease of ≥ 20 mmHg
 - > 90–100 mmHg and an increase of ≥ 20 mmHg
 - > 100 mmHg and an increase of ≥ 20 mmHg
- pulse rate:
 - < 60 bpm and a decrease of ≥ 15 bpm
 - > 100 bpm and an increase of ≥ 15 bpm
- change from baseline body weight:
 - a decrease of:
 - > 7–10%
 - > 10–20%
 - > 20%
 - an increase of:
 - > 7–10%
 - > 10–20%
 - > 20%

7.9.6 Physical findings and other observations

Special situations and physical examination findings will be summarised by treatment group using descriptive statistics.

7.10 Additional analyses

7.10.1 Prior and concomitant treatments

Prior and concomitant treatments will be coded using the anatomical therapeutic chemical (ATC) classification system, WhoDrug version V201909. The number and percentage of subjects using prior (started before baseline) and concomitant (ongoing at end of follow-up, or stopped after baseline) treatments will be summarised by pharmacological subgroup and chemical substance.

7.10.2 Suicidality

Suicidality will be summarised at each visit by treatment group using descriptive statistics. Additionally, suicidality at any point over the course of the study will be described.

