3. OVERALL STUDY DESIGN AND PLAN

This is an open, non-randomised, uncontrolled, multicentre phase III extension study to the REFALS study.

[figure not shown]
The subjects will give informed consent (IC) to continue in this open-label extension study at the 48-week or end-of-study visit of the REFALS (or between these visits). The REFALS end-of-study visit will double as the REFALS-ES baseline visit. Visits to the study centre are flexible but occur at least every 3 months. Subject assessments will be conducted 2 weeks after starting the study treatment and after each change in the dose: such visits may be at study centre or conducted remotely where feasible (see section 6.1.3). A telephone contact will be performed for all subjects 6 weeks after starting the treatment.

The subject may continue the treatment as long as clinically indicated (see withdrawal criteria in section 4.5) or until the study ends.

An end-of-study visit will take place 14-25 days after the last study treatment administration for each subject.

The study design is presented in [Figure 1](#).

Figure 1. Study design

TC = telephone contact, EOS = end-of-study

¹ Dose increased to 1 mg b.i.d. if the 1 mg/day dosing was well tolerated

² Additional visit approx. 2 weeks after any dose change at visit 2

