6.1.2 Procedures during the treatment period

Visits will be performed either by telephone or attendance at the study centre. For simplicity, all visits of the same type involve the same procedures.

Any planned follow-up may take place at the study centre and may occur at any time, but should not be less frequent than every 3 months. The only fixed follow-up points are dose assessment at 2 weeks and telephone contact 6 weeks after start of the study treatment.

Any visit may be performed by telephone provided:

- A reliable measure of resting pulse/heart rate can be obtained and documented.
- The minimum 3-monthly study centre visit schedule is maintained.

In case a subject is no longer able to travel to the study centre, but levosimendan is considered to still be of clinical value, wholly remote monitoring by telephone contacts may be acceptable. This must be agreed in advance by the sponsor and the medical monitor, and an acceptable method of dispensing study treatment must be established.

Procedures during visits are presented in [Table 2](#). The morning dose of study treatment will be administered at the study centre during the study centre visit days. In addition, additional visits or contacts approximately 2 weeks after dose change can occur at any time (see section [6.1.3](#)).

Table 2. Procedures during the treatment period

Time	Study centre visit ¹	Telephone contact
Weight	x	
Pulse/heart rate and BP	x	Pulse/heart rate only
12-lead ECG	x	
Pregnancy test for females of childbearing potential	x	
SVC supine and sitting	x ²	
Study treatment	x	
ALSFRS-R	x	x
Borg CR10 scale	x	
Use of health care and home care resources use and non-medical assistive devices	x	x
Assessment of suicidality	x	x
Status for NIV support, invasive mechanical ventilation by intubation or tracheostomy and survival	x	x
AEs and SAEs	x	x
Medical history and current medical conditions	x	x
Concomitant treatments	x	x

¹ All procedures will be performed pre-dose

² MasterScope used up to 3 months

During the telephone contact a caregiver can take the telephone contact on behalf of the subject in case the subject is unable to communicate verbally due to disease progression.

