6.4.6 Assessment of suicidality

Suicidality will be assessed by asking the following standard questions at each visit:

1. Since the last visit, have you wished you were not alive anymore or had any thoughts about ending your life?
2. Since the last visit, have you done anything or prepared to do anything to end your life?

The second question (2) will be asked only in cases where the answer to the first question (1) has been 'yes'.

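### By-visit suicidality proportions in SAP 7.10.2 are not comparable across visits, because each answer covers the time since the previous contact and that gap runs from about 2 weeks to 3 months

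*SAP*

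**What the plan says.** Protocol 6.4.6 sets two questions: "Since the last visit, have you wished you were not alive anymore or had any thoughts about ending your life" and, only if that is answered yes, "Since the last visit, have you done anything or prepared to do anything to end your life". On timing it says: "Suicidality will be assessed by asking the following standard questions at each visit". Neither question has a fixed look-back period.

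Contacts are unevenly spaced by design. Protocol 6.1.2: "The only fixed follow-up points are dose assessment at 2 weeks and telephone contact 6 weeks after start of the study treatment". Protocol section 3: "Visits to the study centre are flexible but occur at least every 3 months". A footnote to the study design figure adds: "Additional visit approx. 2 weeks after any dose change at visit 2". Protocol 6.1.3 extends the 2-week reassessment to every later dose change. SAP 6.2.9 labels visits after week 6 by the nearest month since baseline.

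SAP 7.10.2 then states: "Suicidality will be summarised at each visit by treatment group using descriptive statistics". It adds a description of suicidality at any point in the study. Neither summary carries an interval length or a time denominator. Separately, SAP 7.9.2 lists Suicide/self-injury as an adverse event of special interest (AESI), with exposure-adjusted incidence rates.

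**The concern.** A longer recall window collects more yes answers at the same underlying rate. The early rows of the table (weeks 2, 4 and 6) cover a few weeks each, while the 3-monthly rows can cover 13 weeks. Subjects within one monthly row can also differ, because a recent dose change shortens the window to about 2 weeks.

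Long-term safety is the primary objective, and the protocol synopsis names suicidality as a safety assessment. Everyone receives levosimendan, so no concurrent untreated group would show that a change over time comes from the visit schedule. A reader could take the step for suicidality emerging with exposure. A real fall after the first weeks could be masked in the same way.

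The at-any-point summary avoids the spacing problem. It has no time denominator, however, and follow-up is open-ended and was cut short (SAP 7.11).

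**Working it through.** The documents give no suicidality rate, so there is no planned figure to reproduce. The rates, prevalences and durations below are assumptions.

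**Recall windows.** Three months at the SAP 6.2.9 conversion is 3 × 30.4375 / 7 = 13.04 weeks. A year is 52.18 weeks.
- Week 2, and week 4 after a dose change at week 2: 2 weeks
- Week 6: 2 weeks after a week 4 contact, otherwise 4 weeks
- Month 3 after the week 6 call: 13.04 − 6 = 7.04 weeks
- Later 3-monthly visits: up to 13.04 weeks

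**Model A: brief episodes at constant rate r.** P(yes) = 1 − exp(−r × w / 52.18), with w in weeks.

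| r per subject-year | 2 wk | 4 wk | 7.04 wk | 13.04 wk | Ratio 13.04 to 2 |
|---|---|---|---|---|---|
| 0.05 | 0.19% | 0.38% | 0.67% | 1.24% | 6.49 |
| 0.10 | 0.38% | 0.76% | 1.34% | 2.47% | 6.45 |
| 0.20 | 0.76% | 1.52% | 2.66% | 4.88% | 6.38 |
| 0.40 | 1.52% | 3.02% | 5.25% | 9.51% | 6.25 |

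If all 227 subjects who started (SAP 7.1) answered, r = 0.10 gives 0.9 expected yes answers for a 2-week window and 5.6 for a 13.04-week window. Once visits are 3 months apart the window stops growing, so the proportion levels off. With closer later visits the ratio falls to about 2.0 at 4-week gaps and 4.0 at 8-week gaps.

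**Model B: thoughts that persist.** With stationary prevalence π and mean duration D weeks, λ = π / ((1 − π) × D) and P(yes) = π + (1 − π) × (1 − exp(−λw)). For π = 2% and D = 4, λ = 0.02 / (0.98 × 4) = 0.0051 per week, giving 2.99% at 2 weeks and 8.31% at 13.04 weeks.

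| D at π = 2% | 2 wk | 13.04 wk | Ratio |
|---|---|---|---|
| 1 wk | 5.92% | 24.9% | 4.2 |
| 4 wk | 2.99% | 8.31% | 2.8 |
| 13 wk | 2.31% | 3.99% | 1.7 |
| 26 wk | 2.15% | 3.00% | 1.4 |
| 52 wk | 2.08% | 2.50% | 1.2 |

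At π = 5% the ratios for 4 to 52 weeks run from 2.7 to 1.2. The direction is upward in every case.

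**Does person-time remove it?** Under Model A with r = 0.10, yes answers divided by time since the previous contact give 9.98, 9.96, 9.93 and 9.88 per 100 subject-years for the four windows. Under Model B, onset among subjects in the no state is λ whatever the window.

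**Who must be at risk.** A first-yes rate that keeps subjects already positive at baseline creates the opposite artefact. Suppose 3% always answer yes and the rest have r = 0.25. The 2-week interval gives 1 − 0.97 × exp(−0.25 × 2 / 52.18) = 3.9% over 2 / 52.18 = 0.038 years, about 102 per 100 subject-years. Later intervals give the assumed 25. With 5% persistent the early figure is about 154. The rate must therefore be restricted to subjects answering no at baseline.

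**Telephone contacts.** In the text available, Protocol Table 1 has no suicidality mark under telephone contact, while Table 2 has one. If calls are excluded, the month 3 window becomes 13.04 − 4 = 9.04 or 13.04 − 2 = 11.04 weeks. At r = 0.10 that gives 1.72% or 2.09% instead of 1.34%, so the step comes earlier.

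**The case against.** The strongest reply is that this is one descriptive table, in a SAP with no hypothesis tests and no planned time trend. Person-time reporting of suicidality events already exists through the Suicide/self-injury AESI, with confidence intervals, rate ratios between prior arms and timing since treatment start. The at-any-point summary is free of the spacing artefact. SAP 7.4 reports duration of exposure separately.

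Part of this stands. It would be wrong to infer that suicidality has no exposure-adjusted analysis, or that the long-term safety conclusion rests on this table. Harm arises only if a reader compares rows over time, but a table laid out by visit invites that. The AESI rate covers only events reported as adverse events, and neither document says that a yes answer must be recorded as one. Neither planned analysis makes the by-visit rows comparable.

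The objection to size also stands. The protocol says planned follow-up "should not be less frequent than every 3 months", so 13 weeks is the longest scheduled gap and not necessarily the typical one. Nothing in the documents favours brief episodes over persistent thoughts.

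**Conclusion.** The by-visit proportions are not comparable across visits. At a constant true rate they step up once, from the 2-week contacts to the 3-monthly visits, and then level off. About 6-fold is an upper bound, for brief episodes and full 3-month gaps. If thoughts last 4 to 52 weeks on average, the step is about 2.8 to 1.2-fold. These figures rest on assumed rates and prevalences; the direction does not.

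Three stronger readings are tempting and are not supported:
- **Proportions keep climbing with time on levosimendan.** They do not, because the scheduled gap is capped at 3 months.
- **The step from baseline can be sized.** It cannot from these documents. The baseline answer comes from the REFALS end-of-study visit, and its recall window depends on REFALS procedures not given here.
- **The comparison of prior arms is biased.** Both arms follow the same schedule, so comparison within a visit is largely unaffected unless dose-change contacts differ by arm.

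The change is worth making because it is cheap and bears on a named safety assessment. It is a reporting correction and does not suggest a safety signal.

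**What to change.** In SAP 7.10.2:

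1. In each by-visit row, show the median and range of days since the previous suicidality assessment.
2. Add new-onset yes per 100 subject-years for question 1, and separately for question 2, by time-on-treatment period and prior arm. Include only subjects answering no at baseline, end each subject's time at the first yes, and show subjects positive at baseline separately. State that question 2, when not asked because question 1 was no, counts as no.

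In the protocol, reconcile Tables 1 and 2 on whether telephone contacts include the suicidality questions. The interval in both items depends on it.

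The cost is SAP wording and one more table. SAP 6.2.9 already uses visit timing since baseline, so no new data are needed. The limitation is that onset can be placed only within the interval between two contacts, so an episode whose interval straddles two periods needs a stated assignment rule.

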7.10.3 COVID-19

The number of subjects affected with any changes to study visit procedures, the number of protocol deviations, and study visits performed as a telephone contact rather than a protocol-specified on-site visit due to COVID-19 will be summarized by treatment group with descriptive statistics.

Both confirmed and suspected infections of COVID-19 will be reported as adverse events. The number of affected subjects will then be found as part of regular AE reporting (see 7.9.2).

In addition to appearing in standard reporting, protocol deviations and AEs related to COVID-19 will also be summarised in a dedicated section.

7.10.4 Combined analyses with the main study

Additional analyses combining the data collected in REFALS with the data collected in REFALS-ES will be performed outside the scope of the clinical study report. This section outlines the currently planned analyses.

The primary population used for combined reporting will be the REFALS safety population.

REFALS study baseline characteristics will be reported for the REFALS-ES safety population.

Descriptive statistics for change from REFALS baseline will be reported for supine SVC, ALSFR-R and Borg endpoints, as well as vital signs (pulse rate, systolic and diastolic blood pressure).

Descriptive statistics for supine SVC and ALSFRS-R endpoints over the course of both studies will be reported in relevant efficacy subgroups identified in the REFALS study.

Random slope models will be fitted using data from both studies to estimate the rate of decline in supine SVC and ALSFRS-R endpoints over an extended follow-up period. A time-by-study-by-arm interaction will be investigated to potentially identify a change in slopes for the placebo arm transitioning over to active treatment for REFALS-ES.

Kaplan-Meier curves will be estimated for the time-to-event endpoints described in 7.5.2.2, and additionally time to invasive ventilation (tracheostomy or intubation) or death, and time to death. Estimation will start from the REFALS baseline and continue until the end of the extension study.

Adverse events and the number of deaths over the course of both studies will be summarised.

7.11 Changes from the clinical study protocol

Due to the results of the main study, and the consequent early termination of this extension study, the scope of reporting has been narrowed.

Most statistical analyses have been removed; instead, we report only descriptive statistics.

The analysis population is referred to as “safety population” rather than “full analysis set” for clarity, as the definition completely aligns with the safety population concept.

Protocol-defined reporting of REFALS baseline characteristics has been moved to additional analyses. Baseline characteristic reporting now reflects status at REFALS-ES baseline.

7.12 Execution of statistical analyses

Statistical analyses will be performed by or under the supervision of Data Science at Orion Pharma.

7.13 Software

Statistical analyses, tables and subject data listings will be performed with SAS[®] for Windows version 9.4 (SAS Institute Inc., Cary, NC, USA).

9. REVISION HISTORY

Version	Date	Summary
0.19	2020-12-16	Cleaned up version for approval. No content changes.
0.18	2020-12-16	Revised based on comments reviewers. Primary change was to add additional combined analyses separately.
0.1	2020-12-04	Initial draft based on REFALS SAP.

10. APPENDICES

10.1 Medical history groups of interest

<https://pallas.orion.fi/webtop/urn.htm?id=090017ff8243e30b&version=0.1>

10.2 Adverse events of special interest

<https://pallas.orion.fi/webtop/urn.htm?id=090017ff8243e35a&version=0.2>
